6.3.4 Subgroup analyses

No subgroup analyses are planned to be performed by CTU Bern.

6.3.5 Additional analyses

No further analyses are planned to be performed by CTU Bern.

6.3.6 Assessment of statistical assumptions

To test model assumptions for continuous secondary outcomes, we will visually check residuals in QQ-plots and residual versus fitted plots.

If model assumptions are violated, transformation of the outcome (e.g. log-transformation), more robust methods (e.g. robust standard errors or robust regression) or non-parametric methods (i.e. Wilcoxon rank-sum test) will be considered.

6.4 Interim analyses

No interim analysis is planned

6.5 Missing data

Missing values in the primary outcome will be categorized as persistent smokers. We intend to obtain full follow-up data on all randomized participants.

Missing data in secondary smoking cessation outcomes will be treated as the primary outcome. If more than 5% of data is missing, all other secondary outcomes will be imputed, assuming values to be missing at random. Each outcome will be imputed separately to ensure robust imputation models. We will use all baseline variables (see Table 2) and outcome measures at all time points as predictors in the imputation models. The two intervention groups will be imputed separately. Variables with more than 50% missing values will not be used for the imputation model. Binary variables with a frequency of less than 5% in one category will be omitted from the predictors, levels of categorical variables with a frequency of less than 5% in one category will be combined with another level in a sensible way. Continuous variables will be log-transformed if it improves normality (checked by Shapiro-Wilks test and QQ plots). If predictors are too highly correlated among each other, we will only consider the predictor which is more strongly correlated with the outcome. In case of missing baseline covariates, ~~W~~we will use multiple imputation by chained equation. We will impute values using predictive mean matching for continuous and ordinal variables, logistic regression for binary variables, and a multinomial regression model for categorical variables with more than two levels. In total, fifty imputed data sets will be generated, which will be analysed as described using Rubin's rules (Rubin 1987). We will compute stabilized inverse probability of censoring weights to take into account potentially informative censoring or outcome data.

CTU Bern	SAP for: ESTxENDS	Version: 4.02.0
----------	-------------------	------------------------

CTU Bern	Template: Statistical Analysis Plan (SAP)	Version: 03
	Code: CS_STA_TEM-11	Valid from: 28.02.2019 5.6.2023

6.6 Safety evaluation

Safety outcomes will be analysed using the ITT and PP set.

The safety analysis will list the number of patients dropping out for both treatment arms, including the reasons, and a list of events for patients dropping out, with the treatment group, relation, grade, type of AE and potential free text.

AEs and SAEs will be summarized by presenting for both treatment arms the number of any AE, any SAE, and the number and percentage of patients with any AE or any SAE.

Further, we will present the

- grade and relation of AEs and SAEs (number of patients with events and the number of events),
- category and grade of AEs and SAEs
- category and relation of AEs and SAEs
- AEs and SAEs stratified by consumption (cigarettes, ENDS, both, none)

6.7 Subproject

Subprojects and further outcomes of interest are registered in clinicaltrials.gov under separate registration numbers. These subprojects and outcomes are not part of the current SAP, nor will they be analysed by CTU Bern.

6.8 Statistical software

All analyses will be done using the current version of Stata (StataCorp. 2019 Stata Statistical Software: Release 16. College Station, TX: StataCorp LLC.). The version of Stata and all used packages will be listed in the statistical report.

6.9 Quality control

The primary analysis of the primary and secondary outcomes will be double programmed by a second, unblinded statistician.

7. Changes from the protocol

The SAP is consistent with principle features of the statistical methods described in the protocol. The SAP only describes the primary and secondary analysis of primary and secondary outcomes. Any deviation from the protocol is detailed hereunder with reason. Further analysis of these outcomes, as well

CTU Bern	SAP for: ESTxENDS	Version: 4-02.0	
CTU Bern	Template: Statistical Analysis Plan (SAP)	Version: 03	
	Code: CS_STA_TEM-11	Valid from: 28-02-2019 5.6.2023	Page 25 of 27

as for additional outcomes are planned by the PI and described in the protocol, but will not be further specified in this SAP.

Table 4: Changes from protocol

Header	Change	Reason
6.1 Outcome definitions	This SAP only focuses on the primary outcome for the main analysis at 6-month follow-up. The primary outcome for the extended follow-ups at 12- and 24-months is not part of this SAP.	Initial outcome defined in the initial protocol was at 6-month follow-up.
2.8. Blinding	All analyses will be unblinded	In unplanned interim analyses, we noticed the low yield of blinded analyses. The study team, aware of allocation took over all analyses.

CTU Bern	SAP for: ESTxENDS	Version: 4-02.0
----------	-------------------	---------------------------------

CTU Bern	Template: Statistical Analysis Plan (SAP)	Version: 03	
	Code: CS_STA_TEM-11	Valid from: 28.02.2019 to 06.2023	Page 26 of 27

8. References

Estimands and SOPs

European Medicines Agency, Committee for Human Medicinal Products; Draft ICH E9 (R1) addendum on estimands and sensitivity analysis in clinical trials to the guideline on statistical principles for clinical trials, step 2b - Revision 1. 30 August 2017.

SOP Data preparation and programming, CS_STA_SOP_05, version 04, 11.09.2018

SOP Statistical data validation, CS_STA_SOP_02, version 03, 11.09.2018

References

StataCorp. 2019. *Stata Statistical Software: Release 16*. College Station, TX: StataCorp LLC.

CTU Bern	SAP for: ESTxENDS	Version: 1.02.0	
CTU Bern	Template: Statistical Analysis Plan (SAP)	Version: 03	
	Code: CS_STA_TEM-11	Valid from: 28.02.2019 6.2023	Page 27 of 27

Changes from originally formulated Statistical analysis plan (SAP)

The originally formulated SAP defined the methods for the main analyses, registered on Clinicaltrials.gov: NCT03589989, to be performed by statisticians at CTU (Clinical trials unit, University of Bern) blinded to randomized groups. During the trial, in the context of the e-cigarette or vaping use-associated lung injury (EVALI) epidemic, there were concerns from scientists and experts worldwide about a potential causal link of ENDS on respiratory outcomes. The study team performed unscheduled interim analyses to verify if participants randomized so far might be harmed by the study products delivered in the intervention group. In the ESTxENDS RCT protocol, we had not formulated interim analyses and had no formal pre-defined stopping rules of the RCT because of futility or potential harm to participants. During these analyses, we exchanged with members of the CTU analysis team and noticed blinding of study allocation would not add substantial benefit to the analyses, making the need for the blinded statistical analyses void. The ESTxENDS research team performed all analyses.

Compared to the last version of the SAP, we made following adjustments:

- Lead statistician: [name], BIHAM, University of Bern
- Statistician performing all analyses: [name], BIHAM, University of Bern
- 2.8. Blinding: All analyses were unblinded to allocated groups.
- 6.5. Missing data: Instead of multiple imputation by chained equation (MICE), we computed stabilized inverse probability of censoring weights since there were no missing data at baseline.

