11.4 Planned Analyses

The statistical analysis of the main results of the trial will be done at CTU Bern by a statistician blinded to the allocation. After the start of the trial but before recruitment ends, a statistical analysis plan will be written. The plan will determine all necessary data preparation steps (e.g. additional validations, generation of new variables), definitions (e.g. analysis sets), and statistical analyses (e.g. models, outputs such as tables and graphs).

All statistical analyses will be presented as effect measure plus 95% confidence interval. A significance level of 5% will be used.

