11.4.4 Interim analyses

No formal interim analysis is planned. We do not anticipate undertaking formal interim analyses in this trial. In particular, even if a significantly large number of participants stop smoking in the intervention group, we will not stop the trial.

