3.1 Data export

Data are entered in the SecuTrial EDC system. Data will be exported using the SecuTrial data export tool, as semicolon delimited file, and are labelled using the codebook provided by the same export by an unblinded statistician. Further, all analysis sets need to be defined by the unblinded statistician, since adherence to the study (needed to define analysis sets) is recorded in the “smoking and e-cigarettes” (cig_ecig) form, from which the treatment group becomes instantly obvious.

The unblinded statistician needs to provide datasets to the blinded statistician without any direct or indirect information about the group allocation but an encoded group allocation variable will be provided.

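### SAP 2.0 drops the blinded main analysis, against protocol 9.0 and its own section 3.1, while the coding of the cessation outcomes and the per-protocol set is still inconsistent

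*Supplement*

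**What the plan says.** Protocol 9.0, section 11.4, is explicit: "The statistical analysis of the main results of the trial will be done at CTU Bern by a statistician blinded to the allocation". Sections 6.1 and 6.2.2 also state that the statisticians are blinded. Section 11.4.4 adds: "No formal interim analysis is planned".

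SAP 2.0 takes the opposite position. Section 2.8 strikes out the blinded statistician. Table 4 in section 7 records the change as "All analyses will be unblinded", gives the reason as "In unplanned interim analyses, we noticed the low yield of blinded analyses", and continues: "The study team, aware of allocation took over all analyses". The closing note on changes to the SAP places this in the period of concern about vaping-related lung injury: "The study team performed unscheduled interim analyses to verify if participants randomized so far might be harmed". It says that the team "noticed blinding of study allocation would not add substantial benefit to the analyses", and that the research team then did all the analyses.

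Section 3.1 of the same SAP was not changed. It still reads: "The unblinded statistician needs to provide datasets to the blinded statistician without any direct or indirect information about the group allocation". It also has the unblinded statistician define the analysis sets, because the smoking and e-cigarette form gives the arm away.

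**The concern.** The trial is open-label, and its primary outcome is built by code from several contacts and one of two biomarkers. In that setting a masked analyst is a main protection against coding decisions made with knowledge of which arm they favour. SAP 2.0 removes that protection before the derivations agree with one another, so people who know the allocation must decide how the conflicts are resolved. The stated reason concerns the usefulness of blinded analysis in general and does not say why allocation-aware coding would be free of bias. A harm check does not require unmasking the cessation analysis.

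At stake is whether the reported quit rates rest on rules chosen without sight of their effect on the arms. The blinded main analysis that the protocol still promises also no longer exists.

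**Working it through.** **1. Who analyses.**
- Protocol 9.0, 6.1, 6.2.2 and 11.4: blinded statisticians for the main analysis.
- SAP 2.0, 3.1: a blinded statistician receives a coded dataset.
- SAP 2.0, 2.8 and Table 4: no blinded statistician; the study team analyses.
- SAP 2.0, 6.9: double programming by an unblinded statistician, which does not restore masking.

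The first two cannot be carried out together with the third.

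**2. What is fixed for the primary outcome.** Anabasine below 3 ng/ml (6.1); CO below 10 as the fallback (Table 3 and protocol 5.1); all randomised participants, chi-square test, Wilson, Koopman and Newcombe intervals (4.2.1, 6.3.1); missing counted as smoking (4.3.1, 6.5). Laboratory staff are blinded for anabasine (2.8).

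**3. What is not settled.**
- *Source of the self-report.* SAP 6.1 takes it from the 6-month exam. SAP 2.7 and Table 3 take it from the telephone contacts and month 6. The two differ for anyone who missed a call, or who admitted a lapse at a call but reported none at 6 months. The protocol's change history notes selective withdrawal in the control group, so a rule for missed contacts could fall unequally on the arms.
- *CO fallback.* The Table 3 code for the primary outcome applies the CO limit only when CO is itself missing. Read literally, nobody could be confirmed by CO. The NNAL-validated rows carry the opposite condition, so the intended reading is fairly clear, but the code must still be rewritten.
- *Per-protocol set.* Table 1 describes regular ENDS use in the control group as at least 1 visit and codes it as at least 3. Section 5.6 follows the 1-visit reading.

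**4. Size.** The plan's own target reproduces. With 12% v 19%, two-sided alpha 0.05, power 90% and unpooled variance: n = (1.960 + 1.282)² × (0.12 × 0.88 + 0.19 × 0.81) / 0.07² = 556.5, so 557 per group; 1114 / 0.95 = 1172.6, against the stated 1172. No sample-size figure is in dispute.

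The documents give no count of unclear cases, so two illustrations follow, each on an assumption.
- Suppose 1% to 2% of one arm is coded differently: 6/586 = 1.0 point and 12/586 = 2.0 points. Against the planned 7 points, 1.02/7 = 15% and 2.05/7 = 29%.
- Suppose the more favourable of k codings were always chosen under the null. The error rate is P(max |Z| > 1.96) for k normal test statistics with common correlation r (simulated, 1,000,000 draws):

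| k | r = 0.95 | r = 0.90 | r = 0.80 |
|---|---|---|---|
| 2 | 6.5% | 7.1% | 7.8% |
| 4 | 8.0% | 9.4% | 11.4% |

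The nominal rate is 5%. This describes deliberate selection, so it is an upper illustration for those values of k and r and not an estimate for this trial.

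**The case against.** The strongest reply is that the departure is declared. Section 7 of the SAP exists to list deviations, and Table 4 and the closing note state the change, a reason and the looks. Sections 2.5 and 6.4 say that no interim analysis was planned, which is true. Disclosure deserves credit, but it leaves protocol 11.4 and SAP 3.1 in conflict with 2.8 and does not reduce the risk.

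Second, most of the open-ended wording in the SAP does not reach the primary outcome. Alternative models (6.3.6) concern continuous secondary outcomes. Merging of sparse categories (6.5) concerns predictors in imputation models for outcomes other than cessation. The unfilled entries for anabasine and NNAL in Table 3 are database mapping, with cut-offs already set. This stands, and it confines the point to the three coding conflicts.

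Third, masking was always partial. By the account in 3.1, the form that reveals the arm is also the source of the primary outcome. This stands too: a scrambled arm label is not enough unless the ENDS-use fields are removed.

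Fourth, self-report comes from participants, and the primary biomarker is measured blind. That protects the raw data but not their coding. Under SAP 2.8 the laboratory is not blinded for NNAL, which validates several secondary cessation outcomes.

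**Conclusion.** The point holds for outcome coding and the per-protocol set. SAP 2.0 contradicts the protocol and itself on who analyses, and it hands unsettled cessation coding to people who know the allocation. It should be mended. The size is unknown; the 1 to 2 points above rest on an assumed 1% to 2% of one arm being recoded in one direction.

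Stronger readings are tempting but unsupported:
- *The primary model is open to choice.* It is not; the test, intervals, analysis set and missing-data rule are fixed.
- *The looks inflated the type I error.* They are described as unscheduled harm checks. No efficacy look or stopping rule is reported, and that results were seen by arm is an inference.
- *SAP 1.0 is a clean specification that predates the looks.* The interim analyses are undated. The only dated review of events linked to the lung-injury reports is October 2019, before SAP 1.0 of June 2020.
- *Censoring weights were invented after the looks.* Protocol 11.5 already names them as a sensitivity analysis for missing outcomes.
- *The results were manipulated.* Nothing in the documents shows this.

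**What to change.** 1. Put SAP section 3.1 back in force for the primary and secondary cessation outcomes. Settle one derivation per outcome: the source of the self-report, the handling of missed calls, and a CO fallback that operates when anabasine is missing and CO is present.
2. Have someone without access to allocation finish and freeze that code on data with a scrambled arm label and the ENDS-use fields removed, before unmasking.
3. Fix the per-protocol set by one rule for control-arm ENDS use, the same in text and code, with the set supplied by the unblinded statistician as 3.1 states.
4. Keep censoring weights as a sensitivity analysis for missing outcomes, in line with protocol 11.5.
5. Record in 2.5 and 6.4 that unscheduled looks took place, when, by whom and on which outcomes. Reconcile 2.8, 3.1 and protocol 11.4.

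The closing note reports the analyses as already done. If so, steps 1 to 3 can be carried out as an independent masked recoding, and the report should not describe the main analysis as blinded.

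The coded dataset is already specified, so the cost is SAP wording, removal of the ENDS-use fields, and a short delay between code freeze and unmasking.
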